8 DATA HANDLING CONVENTIONS

8.1 Baseline Definitions or Conventions

Baseline value is defined as the Day 1 (randomization) measurement. If the Day 1 measurement is not available, the last non-missing pre-randomization measurement will be used as the baseline value.

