  - b. If the patient's disease-specific PAH therapy does not include a PDE-5i, the use of PDE-5i as needed for erectile dysfunction (ED) is permitted as long as the patient has not taken a dose within 48-hours of any Baseline or study related efficacy assessment. In addition, the patient must not take more than 8 sildenafil tablets, 6 vardenafil, or 4 tadalafil tablets per month for ED.
  - c. Patients may be on **one** agent active in the NO pathway, either a PDE5i or a sGCs at stable dose (but not both)
- 8. Has a 6MWT distance of ≥100 meters and ≤500 meters, and within 15% of each other on 2 consecutive tests on different days during Screening
- 9. Has PFTs within 6 months prior to the start of Screening with no evidence of significant parenchymal lung disease. PFTs will be performed as part of screening procedures, if data within 6 months of Screening is not available. Significant evidence of parenchymal lung disease is defined as:
  - a. Forced expiratory volume in 1 second (FEV1)  $\leq$ 70% (predicted) (prebronchodilators); or
  - b. Forced expiratory volume in 1 second/forced vital capacity ratio (FEV₁/FVC) ≤70% (pre-bronchodilators); or
  - c. Total lung capacity (TLC) < 70% (predicted).
- 10. Has no evidence of thromboembolic disease (i.e. should note "normal" or "low probability" for pulmonary embolism) as determined by ventilation-perfusion (V/Q) lung scan or pulmonary angiogram within 5 years prior to Screening
  - V/Q scanning is preferred, but if unavailable, spiral/helical/electron beam computed tomography (CT) angiography is acceptable in patients with NO history of venous thromboembolic disease
  - If V/Q scan is unavailable and patient has a prior history of venous thromboembolic disease, then selective pulmonary angiography is required to exclude chronic thromboembolic disease
  - If a V/Q scan is abnormal (i.e. anything other than "normal" or "low probability"), then a selective pulmonary angiography must be conducted to exclude chronic thromboembolic disease

- All required tests must be performed prior to Screening or such tests may be requested if clinically indicated to exclude chronic thromboembolic pulmonary hypertension

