## 5.9 Randomization

#### 5.9.1 Randomization

Approximately 60 patients will be randomized for entry into the study using an Interactive Web Randomization System (IWRS). Patients will be randomized to either APD811 or placebo in a 2:1 ratio.

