# 9.5.2 Statistical Analyses of Efficacy Measurements

## 9.5.2.1 Primary Efficacy Analysis

The primary endpoints are listed below:

- Change from baseline in PVR after 22 weeks of treatment
- Change from baseline in 6 MWD after 22 weeks of treatment.

The primary efficacy hypothesis regarding the superiority of APD811 to placebo will be assessed in a stepwise manner. First, the statistical significance of APD811 versus placebo result will be determined for the change from baseline in PVR at the end of 22 weeks of treatment. If the result is significant (p < 0.05, two-sided), the primary hypothesis will be considered satisfied and this study will be declared positive. Subsequently, the change from baseline in 6MWD will only be tested if the change from baseline in PVR is significant. This testing procedure preserves the overall Type I error rate for testing the primary efficacy hypothesis.

An analysis of covariance (ANCOVA) model with baseline PVR as a covariate and treatment and baseline WHO/NYHA functional class as factors will be used to assess the effect of APD811 on change from baseline in PVR. Missing values will be imputed using the last observation carried forward (LOCF) method. Assumptions for the analysis of covariance will be checked, and if not satisfied, parametric analyses will be corroborated with nonparametric analyses or with appropriate data transformations if necessary (i.e., log transformation).

Six minute walking distance (6MWD) will be analyzed using the above ANCOVA method described for PVR, substituting the relevant baseline measurement as the covariate. Missing values will be imputed with last observation carried forward, except if any patient withdraws early due to death or due to clinical worsening without a 6MWT being measured at a termination visit, a worst value of 0 for 6MWD will be imputed.

Note that testing for secondary and exploratory endpoints will proceed only if the comparison for the change from baseline in PVR is significant.

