An analysis of covariance (ANCOVA) model with baseline PVR as a covariate and treatment and baseline WHO/NYHA functional class (II vs, III or IV) and baseline background PAH therapy (With ERA vs. Without ERA) as factors will be used to assess the effect of APD811 on change from baseline in PVR. LSM means for the treatments and the treatment effect and LS Mean difference between treatment will be displayed with 95% CIs and the two-sided p-value will be displayed. The normality of the model residuals will be assessed using Shapiro-Wilks test. Assumptions for the analysis of covariance will be checked, and if not satisfied, parametric analyses will be corroborated with appropriate nonparametric analyses, such as the Wilcoxon rank sum test stratified by baseline WHO/NYHA functional class (II vs, III or IV) and baseline background PAH therapy (With ERA vs. Without ERA). The Hodges-Lehmann estimation of location shift and confidence interval will be produced. If the model residuals is not normally distributed, ANCOVA analysis based on log-transformed data will be performed.

Six minute walking distance (6MWD) will be analyzed using the above ANCOVA method described for PVR, substituting the 6MWD baseline measurement as the covariate. Assumptions for the analysis of covariance will be checked, and if not satisfied, parametric analyses will be corroborated with nonparametric analyses, such as the Wilcoxon rank sum test stratified by baseline WHO/NYHA functional class (II vs, III or IV) and baseline background PAH therapy (With ERA vs. Without ERA). The Hodges-Lehmann estimation of location shift and confidence interval will be produced.

Note that formal testing for secondary and exploratory endpoints will proceed only if the comparison for the change from baseline in PVR is significant. In the event that the treatment effect for PVR is non-significant all subsequent testing of other endpoints will be interpreted only in an exploratory, rather than confirmatory manner.

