7 STATISTICAL TECHNICAL ISSUES

7.1 Planned Statistical Power and Sample Size

For the APD811 versus placebo comparison, 28 patients in the APD811 group and 14 patients in the placebo group will have 90% power to detect a between-treatment difference of 350 dyn·s·cm⁻⁵ in PVR. This calculation was based upon the pooled SD estimate of 320.3 dyn·s·cm⁻⁵ for the mean change from baseline in PVR at Week 17 observed in the selexipag phase 2 study.

Assuming that up to 30% of patients may drop out of the trial before a post-randomization repeat RHC is performed, 40 patients will be randomized to the APD811 group and 20 patients will be randomized to the placebo group. For 6MWD, 40 patients in APD811 group and 20 patients in the placebo group will have 80% power to detect a between-treatment difference of 50 meters in 6MWD assuming pooled SD estimate of 65 meters.

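### The 6MWD models adjust for the Day 1 walk only; adding the mean of the two screening walks as a covariate would recover a small amount of unused precision.

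*SAP*

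**What the plan says.** Protocol 4.2 (inclusion criterion 8) requires two screening walks that are "within 15% of each other on 2 consecutive tests on different days during Screening", each between 100 and 500 m. Protocol Table 1 adds a pre-dose walk on Day 1.

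SAP 8.1: "Baseline value is defined as the Day 1 (randomization) measurement". An earlier value is used only as a substitute when Day 1 is missing. The window rule in SAP 8.2 maps everything up to Day 1 to baseline and keeps the assessment nearest the target day, so the screening walks drop out.

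SAP 4.3.1 analyses 6MWD with the PVR model, "substituting the 6MWD baseline measurement as the covariate"; the other terms are treatment, functional class and ERA use. The MMRM in SAP 4.3.3 also takes one baseline value. SAP 4.3.1 itself notes that 6MWD is measured at screening. Neither document uses the screening walks in an efficacy model or says why they are left out.

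On size, SAP 7.1 says that "40 patients in APD811 group and 20 patients in the placebo group will have 80% power to detect a between-treatment difference of 50 meters", with an assumed pooled SD of 65 m.

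**The concern.** A single walk is the patient's underlying capacity plus day-to-day noise. Noise in the Day 1 walk enters the change score, and an ANCOVA on that same walk can remove only part of it. The screening walks measure the same quantity, precede randomization and are already in the database. Leaving them out means a slightly wider confidence interval for 6MWD than the collected data allow. 6MWD is the primary endpoint with the lower stated power: 80%, against 90% for PVR.

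**Working it through.** **Inputs from the documents.** 40 and 20 patients, difference 50 m, SD 65 m (SAP 7.1); two-sided 0.05 (Protocol 9.5.2.1). SAP 7.1 does not say whether 65 m is an SD of change or a residual SD; it is read here as the SD of change.

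**Inputs assumed.** Walk-to-walk SD s = 15, 20 or 25 m; between-patient SD τ = 90 m. Neither is in the documents. Taking τ as 70 or 110 m changes the results little.

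**1. The plan's own figure.** Standard error = 65 × √(1/40 + 1/20) = 17.80 m. 50/17.80 = 2.809, and 2.809 − 1.960 = 0.849, giving 80.2% power (78.9% with a t distribution on 58 df). The stated 80% reproduces.

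**2. Gain before estimation cost.** Let walk = true value + error, with Var(true change) = 65² − 2s². The residual variance of the Week 22 walk, given k exchangeable pre-treatment walks, is

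V(k) = τ² + (65² − 2s²) + s² − τ⁴/(τ² + s²/k).

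The Day 1 walk and the screening mean, each with its own slope, reach V(3) in the population.

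| s (m) | V(1) | V(3) | Fall |
|---|---|---|---|
| 15 | 4218.9 | 4074.3 | 3.4% |
| 20 | 4206.2 | 3956.2 | 5.9% |
| 25 | 4180.2 | 3803.1 | 9.0% |

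**3. Cost of the extra slope.** With N patients and q covariates, estimating the slopes inflates the variance of the treatment estimate by about (N − 3)/(N − q − 3). The planned model has q = 3 (Day 1 walk, functional class, ERA use): 57/54. With the screening mean q = 4: 57/53. The ratio is 54/53 = 1.019, so about 1.9% is given back.

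| s (m) | Net variance ratio | Net fall | Effective SD from 65 m | Power (normal) |
|---|---|---|---|---|
| 15 | 0.966 × 1.019 = 0.984 | 1.6% | 64.5 | 80.8% |
| 20 | 0.941 × 1.019 = 0.958 | 4.2% | 63.6 | 81.8% |
| 25 | 0.910 × 1.019 = 0.927 | 7.3% | 62.6 | 83.1% |

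Simulating the fitted models in 40 and 20 patients agrees: about 2%, 4% and 8%, or roughly 0.5, 2 and 3 power points.

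**4. Effect of the 0 m rule.** SAP 4.3.1 imputes 0 m after withdrawal for death or clinical worsening without a termination walk. Assume a pre-treatment mean of 350 m, so a Week 22 mean of about 350 + 50 × 40/60 = 383 m. A fraction p of zeros then adds about p(1 − p) × 383² to the residual variance.

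- One patient in 60 adds about 2,400. At s = 15, 20 and 25 m the falls are 145/6,619 = 2.2%, 250/6,606 = 3.8% and 377/6,580 = 5.7%. Net of the 1.9%, these are about 0.3%, 2% and 4%.
- Two patients add about 4,700. The net changes are about zero, 1% and 2%.

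Simulation gives the same picture: between about zero and 3 to 4%.

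**5. Replacing the Day 1 covariate instead.** If the outcome stays change from Day 1 and the only walk covariate is the three-walk mean, the residual variance is 65² − (s²/3)²/(τ² + s²/3). At s = 20 m this is 4225 − 133.3²/8233.3 = 4222.8, slightly above the planned model's 4206.2. There is no gain.

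**6. A wider view of the assumptions.** Let ρ be the correlation of one pre-treatment walk with Week 22, and r the correlation between pre-treatment walks. The variance ratio before cost is [1 − 3ρ²/(1 + 2r)]/(1 − ρ²). Over ρ 0.5 to 0.8 and r 0.85 to 0.95, the fall runs from about 1% to 20%. After the 1.9% cost, the low end is a loss of just under 1% (0.989 × 1.019 = 1.008). The high end needs very noisy walks: with equal variances, 65²/(2 × 0.2) × 0.15 = 1584, a walk SD of about 40 m.

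**The case against.** The strongest objection is that this is a preference. Change from Day 1 with the Day 1 walk as covariate is unbiased, prespecified and executable, and the study is declared positive on PVR alone. That stands: a reader might infer that the planned ANCOVA or the 80% power is wrong, and the documents support neither.

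A second objection is to the size. A reader might take the 3%, 6% and 9% of step 2 as the benefit. That ignores the slope that must be estimated and the 0 m rule. Both are real, and the net figures replace those. Learning effects that differ between patients would weaken the covariate further, without biasing the comparison.

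Third, a reader might add that 6MWD needs the help because SAP 7.1 applies its drop-out allowance only to PVR. That does not support the point. The 30% concerns patients without a repeat RHC. LOCF and zero imputation keep most drop-outs in the 6MWD analysis, and an extra covariate would not repair such a gap.

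One objection does not stand: that the 15% agreement rule removes the gain by selecting consistent walkers. Simulating that rule and the 100 to 500 m range left the falls before cost at about 3.4%, 5.8% and 8.6%, because noise on Day 1 and at Week 22 is not selected on.

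**Conclusion.** The point holds as an optional improvement. The planned 6MWD analysis is valid, but it leaves some precision unused. The likely net fall in variance is about 2% to 8% (0.5 to 3 power points) for a walk-to-walk SD of 15 to 25 m, and between about zero and 3 to 4% if one or two patients are set to 0 m. These figures rest on assumed walk variability, on reading 65 m as the SD of change, and on treating the three pre-treatment walks as exchangeable. The documents fix none of these. A narrower interval is therefore likely but not assured.

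**What to change.** In SAP 4.3.1 and 4.3.3, add the mean of the two screening 6MWDs as a further covariate in the 6MWD ANCOVA and the 6MWD MMRM. Keep change from Day 1 as the outcome, so that the estimand does not change, and keep the Day 1 walk as a covariate. Do not substitute a three-walk mean for it.

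Make the change before any patient is unblinded. Patients who enter the extension are locked and unblinded one at a time (Protocol 5.6.2, SAP 8.3), so a covariate added later could look data-driven.

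The cost is a sentence in each section, one degree of freedom (55 to 54 in the ANCOVA) and a covariate collinear with Day 1. No patients, visits or measurements are added. A learning effect common to both arms does not bias the comparison.

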8.2 Time Points, and Day Ranges

Since it is not always possible for all study participants to come in for their clinic visits on the exact day specified in the protocol schedule, the “Week” of a patient’s visit will be defined by the following relative day ranges. Tables 1 to 3 below give the mapping of relative day ranges to Week.

Table 1 Mapping for Endpoints measured at Day 1, Weeks 5, 10, 14, 18 and 22

Time Point	Target	Study Days
Baseline	Day 1	\leq Day 1
Week 5	Day 35	Days 2 \leq to Days \leq 52
Week 10	Day 70	Days 52 < to Days \leq 84
Week 14	Day 98	Days 84 < to Days \leq 112
Week 18	Day 126	Days 112 < to Days \leq 140
Week 22	Day 154	> Days 140

Table 2 Mapping for Endpoints measured at Day 1, Weeks 10, and 22

Time Point	Target	Study Days
Baseline	Day 1	\leq Day 1
Week 10	Day 70	Days 2 \leq to Days \leq 112
Week 22	Day 154	> Days 112

Table 3 Mapping for Endpoints measured at Day 1 and Week 22

Time Point	Target	Study Days
Baseline	Day 1	\leq Day 1
Week 22	Day 154	> Days 2

If a patient has more than one assessment in a window, the assessment date closest to the target date will be selected. If a patient has 2 assessments that are equidistant from the target date, the later assessment will be selected.

8.3 Description of Data Handling Procedures Prior to Unblinding

All data will be screened, reviewed, and declared clean before data are unblinded according to Novella (Data Management CRO) guidelines and standard operating procedures. At the end of the treatment period and after all Week 22 study assessments are performed, patients who are eligible and who elect to enroll in the APD811-007 study, will continue current treatment through the 3 week (± 1 week) follow-up visit (Week 25). During this 3 week (± 1 week) period, the individual patient database will be locked allowing for subsequent unblinding of the individual patient and enrollment into the APD811-007 OLE Study. For patients who do not enter the extension study, study drug will be stopped after the treatment period at the Week 22, End of Study Visit and their individual patient database will not be locked, frozen or unblinded until the end of the study.

9 CHANGES FROM ANALYSIS PLANNED IN PROTOCOL

The protocol specified that the primary efficacy endpoint, PVR, should be analysed using the Modified Intent-to-Treat Population (MITT). This population consists of all patients randomized who received at least one study dose, have a baseline measurement, and have a post-randomization measurement. However, given that PVR is only measured once post-baseline, this amounts to a completers population and hence subjects who withdraw from the study produce missing data on the primary endpoint.

More recently this approach has been recognized as sub-optimal:

'Although it is possible to list conditions under which an analysis of complete cases provides a valid inference (essentially, conditional MCAR), this method is generally inappropriate for a regulatory setting. When missingness is in the outcome, the MAR assumption is generally weaker and can reduce bias from deviations from MCAR by making use of the information from incomplete data.

*Furthermore, when missingness is appreciable, rejection of incomplete cases will involve a substantial waste of information and increase the potential for significant bias.'*³ (p. 55)

For this reason the changes from the analyses specified in the protocol are:

1. The primary analysis of PVR will be based upon the ITT population defined as consisting of all patients randomized who have a baseline PVR measurement.
2. Missing post-baseline PVR data will be imputed using the method of multiple imputation as outlined in Section 7.4 and detailed in Appendix 4.
3. The original planned analysis therefore becomes a sensitivity analysis in support of the new primary analysis.

The synopsis of protocol describes that ANCOVA model for primary analysis includes baseline PVR as a covariate, and treatment, baseline WHO/NYHA functional class and class of PAH

[figure not shown]
therapy at baseline as factors. The SAP clarifies that WHO/NYHA functional class at baseline (II vs. III or IV), and PAH therapy at baseline (With ERA vs. Without ERA) will be covariates in the models.

Other changes from protocol-specified analyses: the expansion of exploratory analyses specified in Section 4.3.3; addition of sensitivity analyses in dealing with missing data issues in Section 7.4; and clarifications of certain data handling details.

Appendix 1 Schematic of APD811-003 Study Design

Appendix 2 Schedule of Procedures and Visits:

Evaluation ^a	Screen ^b	Dose Titration Period									
		Study Week	0	1 ^b	2 ^b	3	4	5 ^c	6	7	8
Day	-28	1	7	14	21	28	35	42	49	56	63
Informed consent	X										
Medical and social history	X										
PAH history ^d	X										
Physical exam ^e	X										
Vital signs ^f	X	X	X	X	X	X	X	X	X	X	X
Safety ECG (12-lead) ^g	X	X	X	X	X	X	X	X	X	X	X
WHO/NYHA functional class assessment ^h	X	X	X	X	X	X	X	X	X	X	X
Assessment of clinical worsening		X	X	X	X	X	X	X	X	X	X
Clinical laboratory tests ⁱ	X	X ^j		X ^j			X ^j				X ^j
HIV, HBsAg, HCV ^k	X										
DNA Sample ^l		X									

^a Reference to pre-dose and post-dose activities in this schedule apply to the morning dose of study drug.

^b All screening activities are to be completed within 28 days, or less, prior to dosing on Day 1.

^c If a patient reaches the highest dose tolerated prior to Week 9, and no additional dose escalations are planned, the visit schedule may be amended at the investigator's discretion. However, visits at Weeks 1, 2, 5, and 9 of the dose titration period are mandatory.

^d Full history of PAH diagnosis, medications, and associated illness and disease

^e Including height and weight

^f Vital sign measurements (blood pressure, heart rate, respirations, body temperature, and pulse oximetry (SpO₂), taken in supine position after 5-minute rest) will be taken at Screening, pre-dose on Day 1, and pre-dose during each visit in which dose escalation is planned. In addition, blood pressure and heart rate will be taken approximately every hour for the first 4 hours following dose escalation. Vital sign measurements should be taken first if they coincide with the timing of a required blood draw.

^g Safety ECG measurements to be completed at Screening, Day 1, and at Weeks 1 - 9, unless the patient's visit schedule is amended due to reaching highest tolerated dose [see footnote c, ECGs will still be required at mandatory visits (Weeks 2, 5, and 9)]; ECGs will be completed pre-dose and 2 hours post-dose.

^h WHO/NYHA functional class will be assessed **pre-dose** at all visits.

ⁱ Clinical laboratory tests will include hematology, serum chemistry, coagulation, and urinalysis and will be taken at Screening, Day 1 and Weeks 2, 5, and 9.

^j To be completed **pre-dose**.

^k Patients with HIV-associated PAH may be included in the study with the approval of the medical monitor.

Evaluation ^a	Treatment Period			Transition Period	
				End of Study (EOS) Visit	Follow-up Visit (start of OLE) ±1 week ^b
Study Week	10	14	18	22 ^c	25
Day	70	98	126	154	175
Physical exam				X	X
Safety ECG (12-lead) ^d	X	X	X	X	X
Clinical laboratory tests ^e	X	X	X	X	X
Serum pregnancy test ^f	X	X	X	X	X
Vital signs ^g	X	X	X	X	X
Study drug administration ^{h,i}	←-----→			j ----->	
Six-minute walk test ^k	X	X	X	X	X
Right heart catheterization				X ^l	
BNP/NT-proBNP ^m	X			X	X
Pharmacokinetic blood sample ^a	X	X	X	X	

^a Reference to pre-dose and post-dose activities in this schedule apply to the morning dose of study drug.

^b For patients who terminate early from the study and is unable to return for the follow-up visit at Week 25, AE and concomitant medication follow-up may be conducted by telephone.

^c Patients should have all assessments including RHC, 6MWT and BNP/NT-proBNP completed prior to entering the transition period.

^d Safety ECGs should be completed **pre-dose**.

^e Clinical laboratory tests will include hematology, serum chemistry, coagulation, and urinalysis. Clinical laboratory tests will be completed **pre-dose**.

^f Serum pregnancy test will be completed **pre-dose** at each visit during the treatment period.

^g Vital sign measurements (blood pressure, heart rate, respirations, body temperature, and pulse oximetry, taken in supine position after 5-minute rest) will be taken **pre-dose**.

^h Study drug should be taken with food.

ⁱ On days with scheduled study visits, patients should **not** take their morning dose of study medication at home in order to complete pre-dose study procedures.

^j Patients entering the APD811-007 study will remain on current dose through the transition period. Patients who do not continue into the APD811-007 study will discontinue study medication at Week 22 visit but not prior to undergoing the final RHC, and will return for follow-up visit at Week 25; if the patient is unable return for the follow-up visit, AE and concomitant medication follow-up may be conducted by telephone.

^k 6MWT should be completed **pre-dose** at approximately the same time of day at each designated visit.

^l RHC will be performed as part of Week 22 end-of-study procedures.

^m Blood sample for BNP/NT-proBNP to be taken after 1-hour rest and prior to administration of 6MWT.

